5.2 Variables Used for Stratification of Re-Randomization

At Week 12, subjects are re-randomized in a 1:1 ratio to one of two double-blinded exploratory treatment regimens (clinically adjusted [CA] regimen and adalimumab therapeutic drug monitoring [TDM] regimen). The re-randomization at Week 12 is stratified by induction treatment regimen, clinical response (CR-70) status at Week 12, and decrease in SES-CD > 50% from Baseline per the site investigator reading at Week 12. Among subjects achieving decrease in SES-CD > 50% from Baseline at Week 12, the randomization is further stratified by achievement of an SES-CD ≤ 4 and at least a 2 point reduction versus baseline and no subscore greater than 1 in any individual variable using the Week 12 SES-CD value provided by the site.

The randomization schedule was prepared by the Statistics Department of AbbVie.

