6.0 Analysis Conventions

Definition of Induction Baseline

The Induction Baseline visit date is the date when the first dose of study drug is received and referred to as Day 1 or Week 0. If a subject has not taken any study drug during Induction Study, the randomization date will be used as Day 1. The Baseline value for a variable is defined as the last non-missing value on or before the date of the first dose of study drug.

Definition of Maintenance Baseline

The Maintenance Baseline visit date is the date when the first dose of study drug during Maintenance Study is received and referred to as Day 1 of Maintenance Study or Week 0 of Maintenance Study. If a subject has not taken any study drug during Maintenance Study, the re-randomization date will be used as Day 1. The Maintenance Baseline value for a variable is defined as the last non-missing value on or before Day 1 of Maintenance Study, and after the Induction Baseline.

Definition of Maintenance Final Observation

Final Observation in the 56-week period (44-week double-blind Maintenance Study) is defined as the last non-missing observation collected within 70 days following the last dose of study drug who are re randomized.

Definition of Rx Days (Days Relative to the First Dose of Maintenance Study Drug)

Rx Days are calculated for each time point of interest and it provides a quantitative measure of days between the event and the first dose date. That is, the Rx Day is calculated as the event date minus the date of first dose of study drug plus 1. The Rx Day will be a negative value when the time point of interest is prior to the date of first dose of study drug, and the Rx Day will be a positive value when the time point of interest is after

the first dose date. By this calculation algorithm the first dose day is Rx Day 1 of Maintenance Study, while the day prior to the date of first dose is defined as Rx Day –1 of Maintenance Study (there is no Rx Day 0). Rx Days are used to map actual study visits to the protocol specified study visits.

Dealing with Multiple Measurements Collected on the Same Day

For efficacy related analyses, if multiple measurements for a particular parameter are collected on the same day for the same subject, the average of those measurements will be used.

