Subjects in whom systemic corticosteroids were used at Induction Baseline and initiated rectal corticosteroids during the study will be censored for efficacy assessment, regardless of rectal corticosteroid dose.

The equivalent steroid dose will be determined based on the table below:

Corticosteroid	Equivalent Dose (mg)
Cortisone	25
Hydrocortisone	20
Prednisone	5
Prednisolone	5
Triamcinolone	4.0
Methylprednisolone	4.0
Betamethasone	0.75
Dexamethasone	0.75
Budesonide	1
Beclomethasone	5
Beclometasone	5

Definition of Missing Data Imputation

The following imputation methods will be used to impute missing values in the efficacy analyses. In addition, an observed case analysis will be performed.

Non-Responder Imputation (NRI)

The NRI approach is used for binary efficacy variables. These variables can take values of 'Achieved' or 'Not Achieved' or may be missing for any reason including discontinuation from study. According to the NRI imputation approach, all missing values will be considered as 'Not Achieved.'

Last Observation Carried Forward (LOCF)

For all variables (categorical variables and continuous variables), the following rules will be used for the LOCF approach:

1. Maintenance Baseline and Pre-Maintenance Baseline values will not be used to impute the missing Post-Maintenance Baseline values.

2. Missing values after Study Day 1 will be imputed using the latest non-missing values after Day 1 and prior to the missing value. If there are no non-missing values after Maintenance Baseline, then the LOCF value will be missing.

Mixed-Effect Model Repeated Measure (MMRM)

The MMRM model will be used for continuous efficacy variables with longitudinal data as a sensitivity analysis. The MMRM model includes the Induction baseline values as covariate; randomization strata, region (US versus non-US), treatment, time point and treatment-by-time point interaction as fixed effects; and subjects within treatment as random effect. An unstructured (co)variance structure will be used to model the within-subject error. The comparison at a time point will be the contrast between treatments at that time point.

Observed Case (OC)

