10.2 Efficacy Analyses

This section provides the details of the efficacy analysis for the Maintenance Study.

For these endpoints which are categorical variables, NRI method of imputation will be used for the missing values. LOCF will be used as a sensitivity analysis wherever applicable.

Both LOCF and OC analyses will be performed for continuous endpoints. The LOCF analysis is considered primary for inferential purposes. In addition, Mixed-Effect Model Repeated Measure (MMRM) will be applied as a sensitivity analysis, wherever appropriate, for the longitudinal continuous endpoints.

For endoscopy related endpoints, there will be no LOCF imputation as there is only one post-baseline endoscopy during Maintenance. OC will be used as a sensitivity analysis.

The difference in proportions of subjects between treatment groups will be analyzed using the two-sided Cochran-Mantel-Haenszel (CMH) test adjusted for induction treatment regimen, and decrease in SES-CD > 50% from Induction Baseline per central reading at Week 12. Additionally, the CMH-based two-sided 95% confidence interval (CI) for the difference in the proportions between the treatment groups will be calculated.

The difference in change from Induction Baseline between treatment groups will be analyzed using an ANCOVA model including factors of treatment, induction treatment regimen, decrease in SES-CD > 50% from Induction Baseline per central reading at Week 12 and Induction Baseline values. Parameter estimates with 95% confidence interval and *P*-value will be provided.

All efficacy endpoints for Maintenance Study are non-ranked.

- Proportion of subjects who achieve endoscopic response (SES-CD > 50% from Induction Baseline [or for a Induction Baseline SES-CD of 4, at least a 2 point

reduction from Induction Baseline]) at Week 56 among subjects with endoscopic response at Week 12

- Proportion of subjects who achieve endoscopic remission ($\text{SES-CD} \leq 4$ and at least a 2 point reduction versus Induction Baseline and no subscore greater than 1 in any individual variable) at Week 56 among subjects with endoscopic remission at Week 12.
- Proportion of subjects who achieve endoscopic remission ($\text{SES-CD} \leq 4$ and at least a 2 point reduction versus Induction Baseline and no subscore greater than 1 in any individual variable) at Week 56 among subjects with endoscopic response at Week 12.

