- Proportion of subjects with enhanced clinical response (decrease CDAI \geq 100 points from Induction Baseline) at each scheduled visit in Maintenance Study.
- Proportion of subjects who discontinue corticosteroid use at each scheduled visit in Maintenance Study among subjects taking corticosteroid at Induction Baseline.
- Proportion of subjects who achieve a composite subtotal score of SFPS < 50 at Week 56 who had an SFPS \geq 100 at Induction Baseline.
- Proportion of subjects who achieve SES-CD \leq 3 and at least a 2 point reduction versus Induction Baseline and no subscore greater than 1 in any individual variable at Week 56.
- Proportion of subjects with SES-CD = 0 at Week 56.
- Change from Induction Baseline in fecal calprotectin level at each scheduled visit in Maintenance Study.
- Change from Induction Baseline in hs-CRP at each scheduled visit in Maintenance Study.

- Change in IBDQ total score and individual IBDQ domain scores (bowel, emotional, social, systemic) from Induction Baseline at each scheduled visit in Maintenance Study.
- Change in WPAI from Induction Baseline at each scheduled visit in Maintenance Study.
- Change in EQ-5D from Induction Baseline at each scheduled visit in Maintenance Study.
- Change in CDAI from Induction Baseline at each scheduled visit in Maintenance Study.
- Change in SFPS from Induction Baseline at each scheduled visit in Maintenance Study.
- Change in Abdominal Pain Rating Scale score from Induction Baseline at each scheduled visit in Maintenance Study.
- Change in Bristol Stool Chart score from Induction Baseline at each scheduled visit in Maintenance Study.
- Proportion of subjects who achieve CDAI remission ($CDAI < 150$) at each scheduled visit in Maintenance Study.
- Proportion of subjects who achieve SFPS remission ($SFPS < 50$) at each scheduled visit in Maintenance Study.
- Proportion of subjects with major CD related event (e.g., hospitalization, bowel surgery, abscess drainage) in Maintenance Study.
- Proportion of subjects with no draining fistulas at Week 56 among subjects with draining fistula at Induction Baseline.
- Proportion of subjects in each treatment group with $> 50\%$ reduction from Induction Baseline in the number of draining fistulas at Week 56 among subjects with draining fistula at Induction Baseline.
- Resolution of extra-intestinal manifestations at each scheduled visit in Maintenance Study.

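### The maintenance ANCOVA and MMRM omit the Week 12 value of the endpoint being analysed, although CA and TDM are randomised at Week 12: an avoidable loss of precision in exploratory comparisons

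*SAP*

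**What the plan says.** Maintenance SAP 5.2 sets the starting point of the comparison: "At Week 12, subjects are re-randomized in a 1:1 ratio to one of two double-blinded exploratory treatment regimens". The same section lists the strata: "The re-randomization at Week 12 is stratified by induction treatment regimen, clinical response (CR-70) status at Week 12, and decrease in SES-CD > 50"% by site reading, with a further endoscopic sub-stratum among those who meet that criterion.

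Section 6.0 defines the pre-randomisation value for this stage: "The Maintenance Baseline value for a variable is defined as the last non-missing value on or before Day 1 of Maintenance Study". It adds that the value must come after the Induction Baseline.

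The models then use the other baseline. Section 10.2 says: "The difference in change from Induction Baseline between treatment groups will be analyzed using an ANCOVA model including factors of treatment, induction treatment regimen". The remaining terms are the binary Week 12 endoscopic response and the Week 0 value: "decrease in SES-CD > 50% from Induction Baseline per central reading at Week 12 and Induction Baseline values". The sensitivity model in section 6.0 reads: "The MMRM model includes the Induction baseline values as covariate; randomization strata, region (US versus non-US), treatment, time point", followed by the treatment-by-time interaction.

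The continuous endpoints in section 10.2 all run from Week 0, for example "Change in CDAI from Induction Baseline at each scheduled visit in Maintenance Study". The others are SFPS, IBDQ, WPAI, EQ-5D, hs-CRP, fecal calprotectin, the abdominal pain rating and the Bristol score. None is a change in SES-CD.

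Protocol 8.1.4.3 asks for adjustment for baseline values and the stratification variables in maintenance, without saying which baseline.

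**The concern.** For a comparison randomised at Week 12, the natural pre-treatment covariate is the subject's Week 12 value of the outcome. By then everyone has had 12 weeks of active induction, so subjects with the same Week 0 value can differ widely. Those differences are known before CA or TDM is assigned, and some of them will persist to Week 56.

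The planned models see Week 12 status mainly through one yes/no endoscopic factor (ANCOVA) or the strata (MMRM). Because no change endpoint is an SES-CD change, that factor is never the Week 12 value of the variable under analysis. What it leaves behind stays as residual noise, and a chance CA–TDM difference at Week 12 passes in part into the later comparison.

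At stake is the width of the intervals. Section 4.3 sets no sample size for this stage, so precision is whatever enrolment and the model deliver, while section 10.2 still promises 95% intervals and P-values.

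**Working it through.** The plan gives no power, standard deviation, correlation or expected size for the maintenance comparison, so there is no stated figure to reproduce. What follows is an illustration.

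**From the documents:** 1:1 allocation at Week 12 (Maintenance SAP 5.2); the covariates quoted above (10.2 and 6.0); two-sided 0.05 tests (10.1); a primary population of Week 12 CR-70 responders (5.1).

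**Assumed, not in the documents:**
- outcome SD of 1
- corr(Week 0, Week 12) = 0.3 and corr(Week 0, Week 56) = 0.2
- r = corr(Week 12, Week 56), from 0.3 to 0.7
- e = corr(endoscopic factor, Week 12 value) = 0.2 or 0.4
- corr(factor, Week 56) = e·r + 0.1, and corr(factor, Week 0) = 0
- induction regimen explains no further variance
- 100 to 200 subjects per arm

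**Step 1: change or raw value.** With the Week 0 value as a covariate, subtracting it from the outcome only shifts its own coefficient by 1. The treatment estimate is the same, so reporting change from Week 0 is not the problem.

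**Step 2: formulas.**
- Residual variance, planned ANCOVA: Vp = 1 − 0.2² − (e·r + 0.1)²
- Week 12 variance left by the planned covariates: L = 1 − 0.3² − e², which is 0.87 (e = 0.2) or 0.75 (e = 0.4)
- Slope on the Week 12 value: b = [r − 0.3×0.2 − e(e·r + 0.1)] / L
- Residual variance with Week 12 added: Vn = Vp − b²L
- Interval width ratio: √(Vn/Vp)

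**Step 3: one case in full (r = 0.5, e = 0.2).** Vp = 1 − 0.04 − 0.04 = 0.920. b = (0.5 − 0.06 − 0.04)/0.87 = 0.46. Vn = 0.920 − 0.40²/0.87 = 0.736. The ratio is 0.800, and √0.800 = 0.894, so the interval is 10.6% narrower.

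| r | e | Vp | Vn | Vn/Vp | Interval narrower by | b |
|---|---|---|---|---|---|---|
| 0.3 | 0.2 | 0.934 | 0.885 | 0.947 | 2.7% | 0.24 |
| 0.3 | 0.4 | 0.912 | 0.881 | 0.966 | 1.7% | 0.20 |
| 0.5 | 0.2 | 0.920 | 0.736 | 0.800 | 10.6% | 0.46 |
| 0.5 | 0.4 | 0.870 | 0.733 | 0.843 | 8.2% | 0.43 |
| 0.7 | 0.2 | 0.902 | 0.500 | 0.554 | 25.6% | 0.68 |
| 0.7 | 0.4 | 0.816 | 0.498 | 0.611 | 21.9% | 0.65 |

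A model with Week 0 alone would leave 1 − 0.2² = 0.960, so the endoscopic factor does some work. It must be in the comparator: at r = 0.5, e = 0.2, 0.736/0.960 = 0.767 would overstate the gain relative to 0.800.

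**Step 4: chance imbalance.** The CA–TDM difference in a Week 12 value has SE √(2/n): 0.141, 0.115 and 0.100 SD at 100, 150 and 200 per arm, or 95% ranges of about ±0.28, ±0.23 and ±0.20. The planned covariates shrink this by √L (0.87 to 0.93), and a fraction b of what remains reaches Week 56. At 150 per arm and r = 0.5: 0.226×0.93×0.46 = 0.10 SD, or 0.226×0.87×0.43 = 0.08 SD.

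**Step 5: simulation.** There were 2,000 runs per setting with 150 per arm, balanced within the endoscopic factor (dichotomised from a normal variable with e = 0.4). Power for a 0.3 SD effect went from 76% to 77% (r = 0.3), 78% to 86% (0.5) and 80% to 95% (0.7). With no effect, rejection was 3.9–5.3% under the planned model and 4.2–5.8% with Week 12 added. The simulation error is √(0.05×0.95/2000) = 0.5 percentage points, so both are compatible with 5%.

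**The case against.** The strongest reply is that the plan already handles Week 12 status and that little depends on the rest. Re-randomisation is stratified on Week 12 clinical and endoscopic response. The ANCOVA carries the endoscopic factor and induction regimen; the MMRM carries the strata and region. The primary population is limited to CR-70 responders, which narrows the spread, for CDAI above all. Escalation driven by CDAI or hs-CRP could weaken the link between Week 12 and Week 56. The endpoints are exploratory and non-ranked, no power is claimed, and many are proportions analysed by CMH, which this change does not touch.

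Much of that stands. A reader might infer that the models adjust for nothing but the Week 0 value; the quoted sentences show otherwise. A reader might also expect the greatest harm at Weeks 14 and 20. But Table 4 of the Maintenance SAP gives hs-CRP, calprotectin, abdominal pain, IBDQ, EQ-5D and WPAI windows only at Weeks 26, 40 and 56. Dose adjustment begins no earlier than Week 14 in either arm, and the stated objective is Week 56.

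What does not stand is that these safeguards replace the covariate. Within a responder-only set, CR-70 status is constant and adjusts for nothing. Entry CDAI runs to 450, so a responder can still have a Week 12 CDAI of 450 − 70 = 380. Responder status also says nothing direct about hs-CRP, calprotectin or quality of life. Under the assumptions above, 75–87% of the Week 12 variance is left unadjusted.

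**Conclusion.** The point holds as one of efficiency. Neither maintenance model contains the Week 12 value of the analysed endpoint, although the SAP defines it and the comparison starts there. The effect is wider intervals than necessary and carry-over of about 0.20 to 0.68 of any Week 12 imbalance that the planned covariates leave.

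The gain could be negligible (3–5% of residual variance at r = 0.3) or substantial (39–45% at r = 0.7). The documents supply neither the correlations nor the size of the responder set, so no single figure, and no equivalent number of extra subjects, can be claimed.

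A reader might go further and infer that the maintenance effect is biased or the tests invalid. The documents do not support that. Randomisation at Week 12 protects the contrast whichever baseline is used, adjusting a change from Week 0 for Week 0 is legitimate, and simulated type I error stays near 5% in both models. No confirmatory claim depends on these endpoints.

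**What to change.** In Maintenance SAP 10.2 (ANCOVA) and 6.0 (MMRM), add the Maintenance Baseline value of the same variable as a covariate for every continuous change endpoint. Keep the Week 0 value and all existing factors, and go on reporting change from Induction Baseline; by Step 1 the treatment contrast does not depend on that choice. Protocol 8.1.4.3 leaves room for this because it does not specify the baseline.

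The cost is one term per model, using data already scheduled and a value already defined. The small downside is that a missing Week 12 value needs a rule that ignores treatment arm, such as the stratum mean. The need should be limited: the SAP definition already takes the last non-missing value after Induction Baseline, and Week 12 CDAI should rarely be missing in a population selected on Week 12 CR-70.

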#### **8.1.4.3 Efficacy Variables for Maintenance Study**

For categorical endpoints, the difference in proportions of subjects between treatment groups will be analyzed using the CMH test adjusted for stratification variables. Additionally, the two-sided 95% confidence interval for the difference in proportions will be provided. The non-responder imputation will be used for subjects with missing data at the endpoint evaluated. The last observation carried forward (LOCF) method will also be used as the sensitivity analyses for the primary and ranked secondary endpoints.

Change from Baseline in continuous ranked and non-ranked secondary endpoints will be analyzed using an ANCOVA model including factors of treatment and adjusting for the baseline values and the stratification variables. For analyses of changes from Baseline

variables, both LOCF and OC analyses will be performed. The LOCF analysis is considered primary for inferential purposes. In addition, Mixed-Effect Model Repeated Measure (MMRM) will be applied, wherever appropriate, as a sensitivity analysis for the longitudinal continuous endpoints.

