Major CD related events will be identified by review of serious adverse events (SAEs) according to the hospitalization adjudication charter. *P* values from both Log-rank test and Cox proportional hazards model will be provided.

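### Maintenance: major CD-related event is compared as a crude proportion under a blanket NRI rule, so subjects who leave with no recorded event count as event-free for all 44 weeks

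*SAP*

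**What the plan says.** The Maintenance SAP, Section 10.2, includes "Proportion of subjects with major CD related event (e.g., hospitalization, bowel surgery, abscess drainage) in Maintenance Study" in its list of non-ranked efficacy endpoints. Four rules bear on it.

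- **Imputation.** Section 10.2: "For these endpoints which are categorical variables, NRI method of imputation will be used for the missing values". Section 6.0 notes that a binary variable may take either value "or may be missing for any reason including discontinuation from study", and continues: "According to the NRI imputation approach, all missing values will be considered as 'Not Achieved". Protocol 8.1.4.3 has the same rule for Maintenance: "The non-responder imputation will be used for subjects with missing data at the endpoint evaluated". None of these places excepts unfavourable endpoints.
- **Comparison.** Section 10.2: "The difference in proportions of subjects between treatment groups will be analyzed using the two-sided Cochran-Mantel-Haenszel (CMH) test", with a CMH-based 95% confidence interval for the difference.
- **Ascertainment.** The end of Section 10.2 says that major CD-related events are found by reviewing serious adverse events under the hospitalization adjudication charter. The next sentence says that P "values from both Log-rank test and Cox proportional hazards model will be provided".
- **Corticosteroid rule.** Section 6.0 treats subjects who start CD-related corticosteroids, or exceed their Induction Baseline dose, as non-responders for categorical endpoints from then on.

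The only time-to-event variable that Section 6.0 of the Maintenance SAP defines is time to dose escalation.

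**The concern.** NRI is conservative when the endpoint is a benefit, because an unknown outcome counts against the treatment. For an event that one wants to avoid, the default value means no event, so the convention works in the opposite direction. The LOCF sensitivity analysis in Section 10.2 does not help, since it would carry the no-event status forward.

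The underlying difficulty is wider than the imputation label. A subject observed for ten weeks without an event and one observed for 44 weeks without an event contribute identically to a crude proportion. The proportion is therefore too low in both arms, and lower in the arm that loses more subjects. A reader comparing the clinically adjusted and therapeutic drug monitoring regimens could see an advantage that reflects shorter observation, or miss a real disadvantage.

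The corticosteroid rule adds an ambiguity. Being a non-responder has no defined meaning for a harm endpoint. Read as not achieved, it could turn an event observed after a corticosteroid increase into no event.

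**Working it through.** **No figure to reproduce.** The Maintenance SAP has no sample size calculation (Section 4.3), and neither document gives an event or dropout rate for this endpoint. What follows is an illustration on assumed inputs.

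**Assumptions.** Exponential event and dropout times over 44 weeks; dropout independent of event risk; the same true 44-week risk p in both arms (10% or 20%); 44-week dropout d of 15% in one arm and 30% in the other.

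**Step 1: no capture after dropout.** With hazards per 44-week period h = −ln(1−p) and g = −ln(1−d), the expected crude proportion is

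h/(h+g) × [1 − (1−p)(1−d)].

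- p = 20% (h = 0.2231), d = 15% (g = 0.1625): 0.5786 × 0.320 = 18.5%.
- p = 20%, d = 30% (g = 0.3567): 0.3848 × 0.440 = 16.9%.
- p = 10% (h = 0.1054), d = 15%: 0.3933 × 0.235 = 9.2%.
- p = 10%, d = 30%: 0.2280 × 0.370 = 8.4%.

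**Step 2: events captured for 70 days after dropout.** Protocol 6.1.4 collects adverse events until 70 days after study drug stops. Let e = 70/308 = 0.227 of the period. The proportion becomes

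1 − exp(−he) + exp(−he) × h/(h+g) × [1 − exp(−(h+g)(1−e))].

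| True risk, both arms | Capture after dropout | 15% dropout | 30% dropout | False difference |
|---|---|---|---|---|
| 20% | none | 18.5% | 16.9% | 1.6 points |
| 20% | 70 days | 19.1% | 18.2% | 1.0 point |
| 10% | none | 9.2% | 8.4% | 0.8 point |
| 10% | 70 days | 9.5% | 9.1% | 0.5 point |

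Differences are taken before rounding. Equal dropout gives a difference of zero, with both proportions still too low.

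**Step 3: masking.** With true risks of 10% v 12% and dropout of 10% v 40%, the Step 1 formula gives 9.5% v 9.4%, so a worse arm looks equal. With 70-day capture (Step 2) it gives 9.7% v 10.4%, so part of the difference is recovered.

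**Step 4: would removing NRI be enough?** If dropouts with no event were left out of the denominator, the proportion would be x/[x + (1−p)(1−d)], where x is the Step 1 result. At p = 20% this gives 0.185/(0.185 + 0.680) = 21.4% and 0.169/(0.169 + 0.560) = 23.2%. Both are now too high, and the false difference is reversed. Neither denominator recovers 20%; follow-up time has to enter the analysis.

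**Step 5: do the log-rank and Cox tests settle it?** In the Induction SAP, Section 10.3 lists time to all-cause and to CD-related hospitalization as endpoints. Section 6.0 there defines time to event, hospitalization included, from Study Day 1, with censoring at discontinuation or Week 12. The Maintenance SAP keeps a sentence on the two tests but lists major CD-related event only as a proportion. For this event it gives no time origin, no censoring rule, no Kaplan-Meier estimate and no hazard ratio. The sentence could also refer to time to dose escalation, the only such variable defined.

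**The case against.** The strongest reply is that NRI is not really what does the damage. Events come from serious adverse event review, not from a visit that a dropout misses, so a subject with nothing on record would usually be classed as having no event rather than as missing. Any crude proportion would then give the Step 1 figures. This stands, and it is why deleting the NRI wording alone would change little.

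A reader might infer that every subject who drops out is counted as event-free. The documents do not support that. An event recorded before leaving counts, including one that caused the departure, and events in the 70-day window are collected. Two limits remain: the SAP does not say whether that window belongs to this endpoint, and Protocol 5.4.1 does not require the call for subjects who start commercial adalimumab.

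A reader might also infer that no time-to-event analysis is planned. The log-rank and Cox sentence directly follows the one on major CD-related events and may well be meant for them. That is a partial answer, since it offers P values without a defined variable or an effect estimate. Likewise, the exposure-adjusted adverse event rates in Section 11.2.1 give some context, but they are not the adjudicated endpoint.

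Finally, the bias is small against sampling error. With an assumed 150 to 200 subjects per arm, the 95% half-width 1.96 × √[p₁(1−p₁)/n + p₂(1−p₂)/n] is 7.5 to 8.6 points at the 20%-risk proportions of Step 1 and 5.6 to 6.4 at the 10%-risk ones. This too stands.

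**Conclusion.** The concern holds as a point about method on an exploratory endpoint. The only effect estimate planned for major CD-related event is a difference in crude proportions in which subjects who leave without a recorded event count as event-free for 44 weeks. Risk is understated in both arms; a false between-arm difference arises only if dropout is unequal or related to event risk. On the assumed inputs that difference is about 0.8 to 1.6 points, or 0.5 to 1.0 with 70-day capture. Informative dropout could change these figures; its effect was not computed.

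It would go too far to say that the plan would probably yield a misleading conclusion about which regimen is safer. All Maintenance endpoints are non-ranked, no confirmatory claim rests on this one, and the documents give no reason to expect one regimen to lose twice as many subjects as the other. The case for change is that a better analysis is available at little cost from dates already recorded.

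**What to change.** In the Maintenance SAP:

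1. State in Sections 6.0 and 10.2 that NRI and the corticosteroid non-responder rule do not apply to major CD-related event.
2. Define in Section 6.0 the time from Maintenance Day 1 to the first adjudicated major CD-related event, censored at the end of observation or Week 56. Say whether the 70 days after discontinuation count as observation.
3. Make this the main analysis in Section 10.2: Kaplan-Meier 44-week risk by arm, a log-rank test stratified by the factors already used for the CMH test, and a Cox hazard ratio with 95% confidence interval. State which endpoints the log-rank and Cox sentence covers.
4. Report the crude proportion descriptively.
5. Because censoring still assumes that dropout is non-informative, add a simple sensitivity analysis that varies the event risk after dropout.

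The proportion requiring dose escalation deserves the same check on the direction of NRI, although it already has a defined time-to-event counterpart.

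The cost is SAP text and slightly more analysis. No new data are needed, since adverse event onset dates are recorded under Protocol 6.1 and adjudication is already planned.
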